Also, long COVID can be regarded as a condition of chronic stress, which could theoretically be associated with disturbances of the hypothalamo-pituitary-adrenal (HPA) axis, although no studies on HPA axis (dys)function in long COVID have been reported yet.

The aims of this study are to describe the standardized evaluation of the psychopathological and neurocognitive function of long COVID patients and their evolution over time; to explore the cross-sectional and longitudinal association

between long COVID symptoms and immunological measures; and to examine the neuro-endocrine (HPA-axis) characteristics of long COVID syndrome.

Three participant groups will be included: 1) long COVID patients with neuropsychological complaints (P), 2) COVID-survivors without persistent complaints (Ca) and 3) healthy volunteers (Cb).

This is a longitudinal study, starting from November 1st 2021. Enrollment will continue for an estimated period of 24 months, depending on the time course of the epidemic curve. Last-patient-in is expected no later than November 1st, 2023. The study will be organized into three work packages (WP1, WP2 and WP3). WP1 includes psychiatric assessments using questionnaires and blood sampling and is the standard WP for every participant. WP2 includes cortisol measurement using saliva sampling for patients and controls from Cb. who do not fulfill specific exclusion criteria (pregnancy, breastfeeding, hormonal therapy with exception of contraceptives, cortisol treatment). Finally, WP3 includes an extensive neurocognitive assessment by a specialized neuropsychologist for both patients and controls from Ca who do not fulfill specific exclusion criteria (sedative medication, pre-existing neurological disease, severe substance abuse, and IQ < 90).

Patients and controls from Ca will be referred mainly by the University Hospital of Antwerp (UZA) and by long COVID patient support groups and enrolled at first visit to UPCD, where follow-up will also take place at 3, 6 and 12 months. WP1 will be performed at each timepoint, while WP2 and WP3 will only be carried out at baseline and 6 months.

Total sample size is estimated on 130 participants.

List of Abbreviations

- ACTH: adrenocorticotrophic hormone
- BACS: brief assessment of cognition in schizophrenia
- BDI: Beck depression index
- Ca: Control group a: COVID-survivors without NP complaints
- CAR: cortisol awakening response
- Cb: Control group b: healthy controls
- CFS: chronic fatigue syndrome

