3.1. Recruitment and study population

Inclusion criteria - patients:

All patients 18-70 years referred to the University Psychiatric Hospital (Campus UZA and Campus Duffel) for psychological and/or cognitive complaints at least >4 weeks following a confirmed diagnosis of COVID-19 infection with a positive PCR test or an antibodies test will be invited to participate in the study. The sample size of the patients is estimated on 50 participants. **The patients have to be examined by their**

treating physician before enrollment to make sure other medical causes for their complaints are excluded. A positive score on at least two domains (psychological / cognitive) is necessary during the screening phase (see 3.3.1).

Inclusion criteria – controls:

Two control groups, one of 30 healthy controls (Cb), another of 50 COVID-19 survivors without persistent complaints (Ca), matched on age, sex and education with the patient group will be included. The participants for Ca will be recruited in UZA and by advertising. The healthy controls (Cb) will be recruited by mailing within the hospital and by advertising. A positive score on maximum one domain (psychological / cognitive) is allowed in the absence of a psychiatric diagnosis (confirmed by the MINI) and when the complaint causes significant distress (which is investigated during the screening phase).

General exclusion criteria:

Participant is unable to read and understand the consent form and patient-reported outcomes, complete study-related procedures, or communicate with the study staff and informed consent cannot realistically be obtained in retrospect or with the help of a competent family member or legal representative.

Exclusion criteria for each subgroup:

- HPA subgroup
 - Participant is pregnant or breastfeeding
 - Participant receives hormonal replacement therapy (contraception is allowed).
 - Participant is treated with cortisol <4 weeks ago
- Neurocognitive assessment:
 - IQ < 90 (screened with Raven Standard Progressive Matrices (Short Form) (RSPM-SF) (39)
 - Participant takes sedative medication
 - Benzodiazepines: Larger than the equivalent of diazepam 10mg per day. Last administration <8 hours prior to the neurocognitive tests.
 - New sedative antipsychotics/antidepressants (<4 weeks)
 - Other medication from DRUID class III (<4 weeks), last administration <8 hours prior to the neurocognitive tests, or causing significant sedation.

- **Severe** substance abuse (alcohol + drugs)

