- Pre-existing neurological diseases

[figure not shown]

Figure 3: Flowchart of the COVID-19 participant inclusion and the work packages (WP). Participants with a confirmed positive PCR test will be included at UZA or UPCD and are classified in the patient group when suffering from neuropsychiatric symptoms for more than 4 weeks. All participants undergo psychiatric assessment and blood sampling on every time point of the study (WP1). Additionally, if patients do not fulfill the exclusion criteria for HPA-axis assessment (pregnancy, breastfeeding, treatment with corticosteroids, hormonal replacement therapy with exception of contraceptives), they are included in the cortisol subgroup (WP2). Finally, all participants, except those treated with class III drugs according to the DRUID classification, those suffering from pre-existing neurological disease or substance abuse and those with an IQ below 90, undergo neurocognitive assessment (WP3).

[figure not shown]

Figure 4: Flowchart of the healthy control inclusion and the work packages (WP). Healthy volunteers can be included in Cb if they were not infected with Sars-CoV-2 in the past and if they do not complain from psychic or cognitive symptoms. If they meet the exclusion criteria for the cortisol testing, they are excluded from the study. WP2 is only performed at baseline.

Study design

General study design:

This is a longitudinal study, which will be organized into three work packages (WP1, WP2 and WP3). Enrollment will continue for an estimated period of 24 months, depending on the time course of the epidemic curve. Last-patient-in is expected no later than November 1st, 2023.

Patients will be referred mainly by the University Hospital of Antwerp (UZA) and enrolled at first visit to the University Psychiatric Hospital (UPCD), where follow-up will also take place at 3, 6 and 12 months. Patients can also be referred by the Flemish long COVID patient support group.

Sample size:

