3.3 Study measurements

To begin with, possible participants will be screened for eligibility before inclusion. First, patients with long COVID symptoms can be referred after completing the screening tests, assessing psychological and cognitive complaints, and can be included if these self-report questionnaires indicate neuropsychiatric symptoms. The control group will perform a screening test to exclude any self-reported psychological or cognitive complaints. If possible, these screening tests will be organized on an online platform.

The data which will be collected for this study which are part of routine clinical practice include the following procedures:

- a baseline clinical psychiatric interview to determine a patient's past and current mental state and psychiatric diagnosis, including psychiatric rating scales
- a baseline neuropsychological evaluation including a standardized test battery (optional)
- extensive neurocognitive tests to examine and document persistent cognitive complaints

Additionally, the following study-related procedures will be performed:

- informed consent and eligibility screening
- blood sample draw (max 35ml per visit)
- saliva cortisol sampling
- additional self-rated scales assessing insomnia, fatigue and psychopathology
- a questionnaire regarding important bio-psycho-social factors such as familial psychiatric antecedents, socio-economic status, social network during the pandemic, personal experience with the COVID-related restrictions, ...

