3.3.2. Neuropsychological assessment

COVID-19 patients with persistent complaints of cognitive disabilities (more than 4 weeks post-infection) in daily life are examined with an extensive neuropsychological test battery (see below) at the outpatient clinic of the University Psychiatric Centre in Duffel and at the University Hospital Antwerp. This battery covers a broad range of reliable and valid tests divided into six cognitive domains: attention, memory, visuospatial functions, language, executive functions and psychomotor speed/coordination. The neuropsychological examination lasts an average of 2 hours per participant. The tests are carried out by the

same experienced neuropsychologist and also follow a standardized sequence. In addition to the neuropsychological assessment, two self-report scales are filled out by each patient. These scales are used to detect possible complaints of fatigue and possible cognitive problems which are experienced by the patient during daily life activities.

A control group of on average 50 COVID-19 survivors without persistent complaints (Ca), matched on age and years of education with the patient group, will also undergo the neuropsychological test battery.

- *Attention*
- The Bourdon-Wiersma Test (BWT) (54) was used to evaluate sustained attention. The primary outcome variables are mean rule time and total omissions.
- The Digit Symbol Coding Subtest from the Wechsler Adult Intelligence Scale (4th Edition) (WAIS-IV (DSC)) (58) is used to assess divided attention and speed of information processing. The total correct symbols and the total errors (or incorrect symbols) within the allowed time of 120 s are used as outcome measures.
- The Dutch version of the Color Word Interference Test from the Delis-Kaplan Executive Function System (D-KEFS (CWI)) (65) is administered to measure focused attention and inhibition of interference (card III) and alternating attention and cognitive flexibility (card IV). The total raw score (total time) and the total uncorrected errors for card III (evaluation of focused attention) and card IV (evaluation of alternating attention) are used as outcome measures
- *Memory*

The Digit Span Subtest from the Wechsler Adult Intelligence Scale (4th Edition) (WAIS-IV (DS)) (58) is used to evaluate working memory. For the digit span forward and the digit span backward we use the total raw score and the longest span (forward or backward) as outcome measures.

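### Section 3.1, read literally, admits a control with one positive domain only if the complaint is distressing; any one-domain allowance also conflicts with 3.3 and Figure 4, and domain can be counted in two ways

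*Combined protocol and SAP*

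**What the plan says.** The control criteria in section 3.1 apply to both Ca (COVID-19 survivors) and Cb (healthy volunteers). They tolerate a positive score on at most one domain, which "is allowed in the absence of a psychiatric diagnosis (confirmed by the MINI) and when the complaint causes significant distress". The sentence adds that distress is looked into at screening.

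Two other places describe control screening:

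- Section 3.3: "The control group will perform a screening test to exclude any self-reported psychological or cognitive complaints".
- Figure 4 legend, for Cb: volunteers can be included if never infected and "if they do not complain from psychic or cognitive symptoms".

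The patient criterion in 3.1 uses the same unit of counting: "A positive score on at least two domains (psychological / cognitive) is necessary during the screening phase", with a pointer to 3.3.1. There, Table 1 has a column headed Domain. Its screening rows include depression, anxiety, trauma, insomnia and neurocognitive as separate entries, plus one composite row for the RMT-20 covering depression, anxiety and trauma together. Most symptom scales have a single cut-off, for example 39 for STAI state and 43 for the CFQ. The BDI-21 has only severity bands: 10-18, 19-29 and 30-63.

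**The concern.** A control group should be at least as free of symptoms as its label says. The distress clause works the other way: it turns distress from a reason to exclude into a condition for entry. It stands in the operative eligibility text, and no other place explicitly corrects it.

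The counting rule matters as much, because the same term separates patients (two or more) from controls (one or none). If two screeners count differently, the same person can be eligible for opposite groups.

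What is at stake is chiefly the comparison of patients with Ca, which the sample size section names as the main control group. Distressed, symptomatic people in Ca would tend to pull its symptom and cognitive scores towards those of the patients. For cortisol the direction is open: section 1.3.3 expects low HPA activity in long COVID but associates depression with high activity. For immune markers the documents give no basis for a direction.

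**Working it through.** The plan has no figure to reproduce here, and no arithmetic applies beyond counting domains. The check sets the rules side by side.

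**Step 1: the distress clause.** Take two control candidates, each with exactly one positive domain and no MINI diagnosis. In the 3.1 sentence the distress condition is introduced by its own conjunction and is not governed by the words that negate the diagnosis. It is therefore a second, positive condition.

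| Rule | Distressed candidate | Undistressed candidate |
|---|---|---|
| 3.1 as written | admitted | not admitted |
| 3.1 with a negation restored | not admitted | admitted |
| 3.3 | excluded | excluded |
| Figure 4 legend (Cb only) | excluded | excluded |

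The first row is the reverse of what a complaint-free control group implies. Rows two to four show that a restored negation leaves a conflict: 3.1 would still admit someone whom 3.3 excludes and, for Cb, whom the Figure 4 legend excludes. It does not help to say that a positive score is not a complaint, because 3.1 itself calls the positive score a complaint.

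**Step 2: counting domains.** Take a COVID-19 survivor clearly positive on depression and anxiety, and negative on trauma, insomnia and the CFQ.

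| Reading | Positive domains | Patient criterion (at least 2) | Control limit (at most 1) |
|---|---|---|---|
| Two categories, as 3.1 suggests in parentheses | 1 (psychological) | not met | within |
| Entries of the Domain column in Table 1 | at least 2 | met | exceeded |

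The count in the second row is at least 2 because the composite RMT-20 row might or might not count in its own right; no rule says how it combines with the separate rows.

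**Step 3: the BDI-21 threshold.** Take someone in the 10-18 band of the BDI-21, with STAI state at 39 and every other scale, including the RMT-20, negative. Counting Table 1 entries, this is 2 domains if the mild band is positive and 1 if it is not. The documents do not say which band is meant, so even a fixed choice of reading does not settle the count.

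**The case against.** The best defence is that the distress clause is an obvious slip. Every general description of the controls, such as "Ca: Control group a: COVID-survivors without NP complaints" in the abbreviation list, points to people without complaints, so literal use is unlikely. The MINI condition also keeps out anyone with a psychiatric diagnosis. Both points limit the probable harm. Neither corrects the rule, and distress below the threshold of a diagnosis still passes the MINI.

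It is also fair that domain is not simply undefined. Section 3.1 gives a gloss, and the patient criterion points to a table with a Domain column. The text even leans towards Table 1: asking for at least two domains is odd if only two exist, and patients may be referred for either kind of complaint. But the gloss is repeated in both the patient and control criteria, and no counting rule is given. The term is therefore ambiguous, not absent.

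Several stronger inferences are not supported:

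- **The Figure 3 legend contradicts 3.1.** It says that participants "are classified in the patient group when suffering from neuropsychiatric symptoms for more than 4 weeks". This summarises classification, and leaving out the two-domain minimum need not contradict it.
- **Distress is not assessed, because Table 1 has no row for it.** Table 1 lists rating scales, and distress can be explored at interview. The text shows only that no method or threshold is stated.
- **One positive score breaches the definition of Ca as free of persistent complaints.** A single screening score need not be a persistent complaint, so this conflict is weaker than the one with 3.3.
- **The planned models are badly affected.** The mixed models in 3.5 relate measured scores to measured predictors, so a wrong group label matters less there. The exposure is in patient-control contrasts, for which 3.5 gives no model.

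**Conclusion.** The point holds and should be fixed. On the text alone, the distress condition is wrong as written. The one-domain allowance conflicts with 3.3 for all controls and with the Figure 4 legend for Cb. The counting of domains is ambiguous in a way that can move one person between the patient group and Ca.

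Applied as written, the likely effect is to narrow patient-versus-Ca differences in symptom and cognitive scores. Its size cannot be computed: the documents give neither the share of controls who would enter with a distressing complaint nor how far they would differ from the rest. Counting possible score patterns would not fill that gap, since patterns are not people and are not equally likely. A reader might infer that distressed people were in fact enrolled as controls. The documents show what the sentence permits, not whom screeners admitted.

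The conclusion assumes only that the sentence is read as it stands. That a negation was dropped is probable, but it remains an inference.

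**What to change.** 1. Correct the clause in 3.1 so that distress is not a condition for admitting a control.
2. Have the sponsor state whether a control may have one positive domain and, if so, under what condition and how distress is judged. Bring 3.1, 3.3 and the Figure 4 legend into line with that decision.
3. State one domain-counting rule for patients and controls alike: which entries count, how the composite RMT-20 row combines with the separate ones, and which BDI-21 band is positive.
4. Check the screening records of enrolled controls against the corrected rule.
5. If some controls do not meet it, patient-control comparisons may be repeated without them as a sensitivity analysis, with balance on age, sex and education shown again.

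If all screen-positive controls are dropped instead, the result must be labelled a bound. BDI-21, STAI, ISI and IES-R serve at screening and again as study scales, so dropping people on those scores mechanically widens symptom differences.

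The cost is one sentence, one counting rule, alignment of three places and a review of existing records. The sensitivity analysis would have fewer controls, and removing them may disturb the matching.

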1.3. Immune disturbances as translational pathways

1.3.1. Systemic immunological disturbance

Large population cohort studies have replicated the finding of systemic immune disturbances (such as but not limited to IL-6 and C-reactive protein (CRP)) in cohorts of patients with depression (19). Longitudinal studies demonstrated the predictive value of these immunomarkers towards clinical outcome and the development of comorbidities such as chronic fatigue, anorexia, insomnia, somatic disease, ... (20–23). Anti-inflammatory agents have been confirmed as valid add-on treatment options to improve depressive symptoms (24). In longitudinal analyses, higher baseline IL-6 levels predicted a subsequent chronic course of depression in women but not in men (25). Similarly, higher baseline IL-6 levels in childhood were associated with depressive and psychotic symptoms at age 18 (26).

Finally, the clinical observation that some patients with long COVID complaints experience an improvement of their NC symptoms following SARS-CoV-2 reinfection or vaccination supports the hypothesis of immune-related pathways involved in the pathophysiology of post-COVID NP complications.

[figure not shown]

Figure 2: Effect of the decrease of systemic inflammation from hospital admission to 3 months follow-up on the pattern of change of depressive symptoms (measured with BDI-13) during follow-up. (7)

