1.4. Insomnia

Genome Wide Association Studies have demonstrated a strong correlation of the genetic risk of insomnia with depression and anxiety (36,37). Furthermore, insomnia has been identified as a primary risk factor for the onset, persistence and relapse of anxiety, depression and PTSD. In a Network Outcome Analysis of 768 individuals without history of depression, *difficulty initiating sleep* was one of only five direct predictors of first-onset major depressive disorder after six years follow-up (38).

Depending on the study methods, in long COVID patients the prevalence of clinically relevant insomnia was estimated between 5% (diagnosis of insomnia disorder in electronic medical records <6m following infection) and 24% (self-rated insomnia symptoms above clinical cut-off at 3-month follow-up). These symptoms could represent an important risk factor in the subsequent development of anxiety and depressive disorders, and a key mechanism underlying cognitive deficits.

2. Research Objectives

- 1) Describe the standardized evaluation of the psychopathological and neurocognitive function of long COVID NP patients and their evolution over time;
- 2) Explore the cross-sectional and longitudinal association between long COVID NP symptoms and immunological measures;
- 3) Define the prevalence and clinical characteristics of insomnia in long COVID NP patients, as well as its correlation to the clinical psychiatric and neurocognitive symptom domains;
- 4) Compare the immunological profile of long COVID NP patients to those of existing cohorts of comparable primary psychiatric conditions and healthy controls;
- 5) To examine the neuro-endocrine (HPA-axis) characteristics of long COVID syndrome

3. Methodology

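### The patient group has no rule that complaints began or worsened after COVID-19, so long-standing psychiatric illness can enter it and pull it towards the primary psychiatric comparators in objective 4

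*Combined protocol and SAP*

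**What the plan says.** Section 3.1 admits to the patient group (P) people aged 18-70 who are referred for "psychological and/or cognitive complaints at least >4 weeks following a confirmed diagnosis of COVID-19 infection". It adds two conditions:

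- "A positive score on at least two domains (psychological / cognitive) is necessary during the screening phase".
- The patient must be seen by the "treating physician before enrollment to make sure other medical causes for their complaints are excluded".

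The Figure 3 caption states the classification more loosely: cases "are classified in the patient group when suffering from neuropsychiatric symptoms for more than 4 weeks".

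For controls, one positive domain "is allowed in the absence of a psychiatric diagnosis (confirmed by the MINI"). Patients face no matching condition. The only pre-existing illness that is excluded appears in the list for neurocognitive testing: "Pre-existing neurological diseases".

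Objective 4 in section 2 is to "Compare the immunological profile of long COVID NP patients to those of existing cohorts of comparable primary psychiatric conditions and healthy controls". Section 1.3.1 says that population studies have replicated "systemic immune disturbances (such as but not limited to IL-6 and C-reactive protein (CRP)) in cohorts of patients with depression".

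Section 3.3.5 lists psychiatric history, infection date and duration of the long COVID symptoms among the data to be collected. Section 3.5 does not name any of them as a covariate, stratum or sensitivity analysis.

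**The concern.** Long COVID as a cause implies that something changed after the infection. The criteria check that complaints are present after it. They do not check that the complaints were absent or milder before it. Recruitment is through a psychiatric hospital, so referrals with an earlier psychiatric disorder are plausible.

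Objective 4 has most at stake. If part of P consists of primary psychiatric illness with an incidental infection, P is being compared partly with its own kind, and a real difference is understated. The patient v control comparisons of immune markers are also exposed, because a disorder that carries its own immune changes can be present in P and is screened out of the controls. The same applies to HERV-W ENV, which section 1.3.2 links to schizophrenia and bipolar disorder and section 3.4 lists as an endpoint.

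**Working it through.** **1. Does any text supply an onset rule?**

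| Text | What it tests | Onset or worsening? |
|---|---|---|
| 3.1, patient criterion | Complaints more than 4 weeks after confirmed infection | No |
| Figure 3 caption | Symptoms for more than 4 weeks | No, and no upper limit on duration |
| 3.1, two-domain screen | Current scale scores | No |
| 3.1, physician check | Other medical causes | Not stated; psychiatric history is not mentioned |
| 1.1, definition of long COVID | Symptoms of COVID-19 after 4 weeks | Implied, but this is background text |
| 3.3 and 3.3.1, interview and MINI | Past and current mental state, diagnosis | Recorded; not used for patient eligibility |
| 3.3.5, clinical records | Psychiatric history, infection date, symptom duration | Recorded only |
| 3.5, longitudinal models | Baseline covariates, not listed | Psychiatric history not named |

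Section 3.5 describes models for associations between symptoms and inflammation or insomnia. It describes no comparison of P with controls or with psychiatric cohorts, so no planned analysis makes the separation either.

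**2. Effect on objective 4.** Let N be the mean marker value in new-onset patients, D the mean in the primary psychiatric cohort, E the mean in patients with pre-existing illness, and q the share of the latter in P. Then

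P - D = (1 - q)(N - D) + q(E - D).

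If the illness is wholly pre-existing, E = D and the observed difference is (1 - q)(N - D). If those patients also carry a COVID-related component, write E - D = w(N - D) with w between 0 and 1. The factor becomes 1 - q(1 - w). For example, q = 0.4 and w = 0.5 gives 1 - 0.4 x 0.5 = 0.8 instead of 0.6. So (1 - q) is the upper limit of the shrinkage for a given q.

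**3. Illustration under assumptions.** The plan's only power figure is a total of 64 for 80.0% power at f2 = 0.15 in a MANOVA. Alpha and the numbers of groups and outcomes are not given, so it cannot be confirmed. It is not shown to be wrong: with alpha 0.05, 3 groups and 6 outcomes, 64 is the smallest total that reaches 80% (80.6%). This point does not depend on it.

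For scale, take the plan's effect size as a two-group difference, d = 2 x sqrt(0.15) = 0.775, and a smaller d = 0.5. Assume 50 patients v 50 comparators (cohort sizes are not given), two-sided alpha 0.05 and w = 0. Power is approximately Phi(d(1 - q) x sqrt(n1 n2/(n1 + n2)) - 1.96). With all 50 patients the root is sqrt(2500/100) = 5. The new-onset columns use 50(1 - q) patients and the undiluted d.

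| q (assumed) | All P, d = 0.775 | New-onset only, d = 0.775 | All P, d = 0.5 | New-onset only, d = 0.5 |
|---|---|---|---|---|
| 0 | 97.2% | 97.2% (n = 50) | 70.5% | 70.5% |
| 20% | 87.3% | 95.5% (n = 40) | 51.6% | 65.4% |
| 40% | 64.2% | 91.8% (n = 30) | 32.3% | 58.1% |

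Under these assumptions dilution costs more power than the smaller new-onset subset does.

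**4. Patients v controls.** With control mean C, P - C = (1 - q)(N - C) + q(E - C). Relative to a purely new-onset group the result shifts by q(E - N). The documents give no value for E or N, so neither the size nor the sign of this shift can be stated for the immune markers.

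**5. HPA axis.** Section 1.3.3 expects hypofunction in long COVID, so N - C points down. It associates hyperactivity with depression, so E - C points up. The two terms have opposite signs, and pre-existing depression tends to cancel the expected difference.

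**The case against.** The intended population is clear. The summary describes P as long COVID patients, section 3.3 speaks of patients with long COVID symptoms, referral runs partly through long COVID support groups, and section 1.1 ties the term to symptoms of COVID-19. The physician check can be read as excluding any cause other than COVID-19, and that physician normally performs the psychiatric interview. The Figure 3 caption belongs to a figure that cannot be seen here; section 3.1 is the operative text. Admitting people with psychiatric history is also defensible in an observational study of routine referrals, since objectives 1 and 3 are descriptive and objective 2 is exploratory.

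Much of this stands as evidence of intent, and the two-domain screen narrows entry further. None of it is a test that a recruiter could apply to decide whether a complaint is new. Whether the word medical covers an earlier psychiatric disorder is left open. The data for a separation are collected, but no analysis uses them.

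A reader might infer that people with long-standing illness do enter in number. The documents show only that they can. A reader might also extend the point to cognition, but section 1.2 reports that previous psychiatric diagnosis did not significantly affect neurocognitive function in the cited cohort, so the immune and HPA comparisons are where it matters most.

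**Conclusion.** The gap is real and should be closed. As written, the criteria let long-standing psychiatric illness count as long COVID. The objective 4 difference would then shrink by up to the share of such patients. That share is not in the documents, and the power figures above are assumptions that show scale; the conclusion rests on the wording of the criteria and on the protocol's own account of immune disturbance in depression.

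Two stronger readings are not supported. The first is that the HPA objective is distorted in the same way as the immune one. Section 1.3.3 points to masking, and objective 5 names no primary psychiatric comparator. The second is that a definite spurious patient v control difference can be calculated. The documents give no marker difference to calculate it from, so for the immune markers the claim stops at possible confounding of unknown size and direction.

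**What to change.** 1. State in section 3.1 and in Figure 3 that the qualifying complaints must have started, or clearly worsened, after the dated SARS-CoV-2 infection, as judged at the psychiatric interview and MINI already performed.
2. Use the psychiatric history, infection date and symptom duration from section 3.3.5 to classify each patient as new-onset or as having a pre-existing disorder that worsened.
3. Pre-specify in section 3.5 the objective 4 comparison, and the patient v control immune and HPA comparisons, in new-onset patients as well as in all patients.
4. Include prior psychiatric disorder (yes/no) as a covariate in the patient v control comparisons.

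Steps 2 to 4 need no new data and can be applied to patients already enrolled. The costs are that some referrals no longer qualify, the new-onset subset is smaller, and onset judged in retrospect carries recall error. The change does not fully remove confounding by current depression, because new-onset depression may carry its own immune changes.
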